## **7. Measurement Analysis**

- i) Calculate mean  $\bar{x}$  and standard teaching Deviation S
- ii) Statistical Processing of the Distribution of Overall Physical Performance
- iii) Test Reliability Analysis

$$r_{\text{信}} = \frac{K}{n} \left| 1 - \frac{\sum_{i=1}^n \tilde{x}_i}{n} \right|$$

- iv) Test Validity Analysis

$$R_{\text{效}} = \frac{\sum (X - \bar{X})(Y - \bar{Y})}{\sqrt{\sum (X - \bar{X})^2 \sum (Y - \bar{Y})^2}} = \frac{1_{XY}}{\sqrt{1_{XX} * 1_{YY}}}$$

$$1_{XX} = \sum X^2 - \frac{(\sum x)^2}{n} \quad 1_{YY} = \sum y^2 - \frac{(\sum Y^2)}{N} \quad 1_{XY} = \sum xy - \frac{(\sum x)(\sum y)}{n}$$

## 8. Distinguish between reliability and validity.

- i) Defines related concepts.

Reliability is one of the factors that researchers need to consider during testing or evaluation. Specifically, it refers to the consistency or stability of test scores (Johnson et al., 2015). In educational testing, reliability refers to the consistency and stability of scores on a set of tests (Huang, 2012). Reliability Coefficient. The reliability of test scores must pass the empirical test. Reliability is usually calculated from some correlation coefficient. The reliability coefficient expresses empirical verification. The correlation coefficient calculated in measuring reliability is the reliability coefficient. A reliability coefficient of 0 means no reliability, a reliability coefficient of +1.00 means the best reliability, and a negative coefficient implies no reliability. The methods to calculate reliability include test-retest reliability, equivalent-form reliability, internal consistency reliability, and inter scorer reliability.

Validity, the accuracy of inferences or explanations derived from test scores. Validity is interpretation and belief based on test scores (AERA, APA, & NCME, 1999; Messick, 1989). Validity requires validity evidence, and validation is a review process to collect valid proof. The valid evidence collected by educational researchers mainly includes content-related evidence. Evidence-based internal structure includes factor analysis, homogeneity, and evidence-based on other variable relationships, such as concurrent evidence. The validity includes external validity and internal validity. Intrinsic validity refers to the range in which results can be accurately explained. External validity refers to the people, situations, and conditions under which the results can be popularized.

- ii) The relationship between them.

The relationship between reliability and validity. Reliability is a necessary condition for validity but not a sufficient condition. There must be reliability to ensure validity. Reliability cannot ensure validity.

iii) Explain how to measure the reliability and validity

First of all, we must do understanding and testing the validity. Reliability and validity are the two essential characteristics measured by "The effect of a 6-weeks content knowledge workshop on written test performance". Reliability is a statistical concept, and reliability is consistency. The measurement method measures each object Consistency of results, the consistency of the results obtained by measuring the same individual at different times (William Wilsmar, 2010). Reliability is related to errors. The greater the error, the lower the reliability, and the smaller the error, the higher the reliability. The measured value of reliability is the reliability coefficient, the reliability coefficient (0-1). Therefore, the error must be reduced during the test of "The effect of a 6-weeks content knowledge workshop on written test performance".

In our study, validity refers to the degree to which an instrument accurately measures what it intends to measure. Three common types of validity for us to consider are content, construct, and criterion validity. Moreover, content validity indicates the extent to which items adequately measure or represent the content of the property or trait that the researcher wishes to measure. Thus, the first step in instrument development is to assess content validity about the effect of a 6-weeks content knowledge workshop on written test performance.

Second of all, another basic feature of measurement is validity. Validity is the degree to which the measuring means should achieve the measuring purpose. Validity is the adequacy of the test or survey results to the measured object, especially to the specific research purpose. The measuring validity includes the basis related to content, calibration, and structure. For example, the validity of "The effect of a 6-weeks content knowledge workshop on written test performance" is directly related to "the basis related to the content." Construct validity indicates the extent to which a measurement method accurately represents a construct in the "The effect of a 6-weeks content knowledge workshop on written test performance" experiment. A latent variable or phenomena can't be measured directly, such as a student's learning attitude and motivation.

**9.Content validity is suitable for evaluating students' achievement tests, and the test content should be based on content knowledge as a sample.**

To improve the research validity, we must do the following:

- i) Define the general concept of content knowledge and identify six types of content knowledge for specific intervention.
- ii) Divide the outline, plan the proportion of each system according to its importance, and make a detailed description as far as possible.
- iii) Determine the proportion of content knowledge of the intervention, and compare its classification with the outline of "content knowledge test preparers of educational examination institutions."

iv) We are formulating an evaluation scale to evaluate the test from all aspects.

Lastly, criterion-related validity indicates the extent to which the instrument's scores correlate with an external criterion. It is usually another measurement from a different tool (concurrent validity) or in the future (predictive validity). The standard teaching size of this type of validity is the correlation coefficient between two measures (Li, 2016). In this study, we must also consider the types of tests for reliability and validity. Therefore, we choose the achievement test. A standard teachingized achievement test is applied in experimental intervention because it ensures reliability and validity. standard teachingized achievement test-written test has been evaluated by three experts in the field of content knowledge from Ohio State University in the United States and three experts in content knowledge in China (Detailed introduction later).

v) Based on explaining how we measure the reliability and validity in my study, we will elaborate on the following three aspects:

First and foremost, in our study, based on the reliability, we will use the test-retest reliability method to evaluate. Test-retention reliability refers to the consistency and stability of test scores in six weeks. For example, test-retest reliability is used to assess the influence of six weeks' content knowledge on students' written test achievement. In the first step, the experimental group was given a test, and then the experimental group was given another test 1-2 weeks later. By analyzing the achievements of two written tests, if the achievements of two written tests are highly correlated, the test scores are credible.

Moreover, the validity. Based on the analysis of content validity. In our study, we defined this method as usually a logical analysis. That is to say, not only it focuses on the six-week content knowledge validity analysis, but it also relies on experts to analyze all the questions in the written test and classifies all the questions bidirectionally according to the content distribution and examination objectives of the written test, thus completing the "two-way breakdown of 6-weeks content knowledge examination". Then, based on the analysis of "Two-way breakdown of 6-weeks content knowledge examination", experts commented and judged the satisfaction of the content validity of written test measurement. "Two-way breakdown of 6-weeks content knowledge examination" reliable and valid analysis. According to the validity and reliability requirement, we completed its design(Yan, 2011). In this process, we should pay attention to the following problems: compare the consistency between the content of the highlighted test and the content knowledge, and divide the proportion according to the content knowledge of 6 weeks. Determine whether the test content fully covers the scope of the conceived content. Examination questions must be consistent with measurement objectives. Students' achievements in 6 weeks' content knowledge will be tested by written tests, requiring objective grading and scoring standard teachings.

In the last place, comprehensive factors. Ensure that the sources of reliability and validity are similar to those of college students majoring in physical education. Master the characteristics of standard

teaching and workshop groups be before the test. The empirical reliability data and validity data were collected before the experiment to prove that the test experiment we chose is suitable for college students majoring in physical education. The reliability coefficient comes from the Journal of educational psychology.

## **10. Experiment the strengths and weaknesses**

### **a) The strengths**

i) True experiments are the most rigorous and robust experimental designs because of equating the groups through random assignment. We randomly sign participants to different conditions of the experimental variable. Individuals in the experimental group (Workshop group) receive the experimental treatment, whereas those in the control group (standard teaching group) do not.

ii) pretest-posttest control-group ensures the equality of experimental (Workshop group) combination control (standard teaching group) group before intervention.

ii) Achievement tests are widely used in educational experiments, and students' achievement tests are the most frequently tested in educational situations. Six weeks' content knowledge is the most basic test for students' written test achievement in an academic position. Generally speaking, after the end of a semester, the achievement tests are conducted, and the achievement tests are used to test later. The scores of students participating in the achievement tests can be compared with the norm data. In this experiment, after learning content knowledge for six weeks, students test it, and the test method and process are the same as achievement tests.

iii) Achievement tests include two types: An academic achievement test and a comprehensive achievement test. A study on the influence of six weeks' content knowledge on complete achievement tests students' achievement. In this study, the content knowledge is classified into six categories, and the comprehensive tests of the six categories meet the comprehensive achievement test standard teachings of achievement tests. The comprehensive achievement test can be either a single test or a complete set of tests. This study's 6-week content knowledge test can use either one of the extensive achievement tests, which is flexible.

iv) Group tests can save human resources and time. We can complete two tests within six weeks and collect 52 students' content, knowledge, achievements, and learning materials within six weeks. Moreover, group tests have been widely used in education.

### **b) The weaknesses**

i) The random distribution in the true experimental pretest-posttest control group cannot ensure 100% equality between the experimental and control groups.

ii) We adopted the equal group experiment method. Therefore, the most significant possibility is to ensure equality between the workshop group and the standard teaching group. Still, we only

achieved equality between the workshop group and the standard teaching group in the total average number. The weakness lies in not achieving equality in the "mean difference" and "standard teaching deviation."

iii) Group test, the interviewee's reaction is not easy to control. Moreover, it is not easy to analyze the influence of individual students' learning motivation, learning fatigue, and other factors in group tests or examinations. Thus, it is not conducive to diagnosing students' learning situations and the specific guidance of students' learning difficulties.

iv) In the whole experimental design, the independent variables only focus on content knowledge, so more interference variables and interference information are excluded. However, it is challenging to eliminate interference factors, which reduces the precise controllability of the experiment.

## 11.Data Collection

Number of written test and Sampling Categories.Number of test papers and sampling categories.categories test paper ( data <100 ) by random sampling ( stratified sampling by class ) (Liu et al., 2001).

### 11.1 Calculate Mean and standard teaching Deviation

Calculate  $\bar{X}$  &  $(S) \bar{X}$  represents the average level of the theory test, and S represents the discrete state of scores.The smaller the S, the more concentrated the performance ( Liu, 2001 ) .

### 11.2 Statistical Processing of the Distribution of Overall Physical Scores

The test performance is standardly distributed, and the test papers are reasonable—the average difficulty of non-standard distribution+—bimodal distribution results from the problem.

## 12.Data Analysis

Table 12. Data Analysis - Base on Hypothesis

Research Objective	Research Hypothesis	Data Analysis
1.Basic theoretical knowledge	1.1 There is significant difference between the control group and the experimental group in the Sports training design written test performance among P E students in China.	Two-way ANOVA
	1.2 There is significant difference between the control group and the experimental group in the Teaching design written test performance among	Two-way ANOVA

	P E students in China.	
2.Health promotion knowledge	2.1 There is significant difference between the control group and the experimental group in the Muscle function system written test performance among PE students in China.	Two-way ANOVA
	2.2 There is significant difference between the control group and the experimental group in the Exercise physiology system written test performance among PE students in China.	Two-way ANOVA
3.Physical exercise knowledge	3.1 There is significant difference between the control group and the experimental group in the Competition venue planning written test performance Among PE students in China.	Two-way ANOVA
	3.2 There is significant difference between the control group and the experimental group in the Referee rules written test performance among PE students in China.	Two-way ANOVA

Based on the research objective, focus on the research hypothesis. To achieve the research hypothesis, we must use t-way ANOVA analyses.

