# **EFFECT OF 6-WEEKS CONTENT KNOWLEDGE WORKSHOP ON WRITTEN TEST PERFORMANCE AMONG PHYSICAL EDUCATION STUDENT IN CHINA**

## **Executive Summary**

[figure not shown]
The employment survey of Chinese students found that it is very difficult for students majoring in physical education to find jobs. The analysis found that the main factor causing employment difficulties is that Chinese students have very low written test achievements. However, content knowledge determines the student's written test achievement. Therefore, to solve student employment difficulties, the student's written test achievement and improving the students' written test achievement through experimental design and quantitative research methods.

This experiment aims to use two different teaching methods to intervene in students' learning and find out which teaching method is more conducive to improving students' written test achievement. The experiment will use a 6-week workshop intervention to enhance students' written test achievement. The experiment is divided into workshop groups and standard teaching groups. The most significant difference between the two groups is that the workshop group has oral links and guarantees. The similarities between the two groups are: The same teacher qualifications; The same intervention time; The same content; The same research objects.

Based on content knowledge learning, content knowledge is divided into six categories for detailed intervention. We will do a 6-week intervention for two groups (workshop style and standard teaching style). After that, we will assess their progress based on writing tests that the Examination agency develops.

The difference between the two is whether there is a video teaching link, and the same is that there are oral links. The entire experiment was carried out in the classroom with the school's consent. Use written exams to check student scores. Students have special teachers responsible for teaching specific content knowledge during class, standard learning after class does not require special care, and the experiment is not risky.

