## **2.Explain in detail the research design that we have employed in this study**

### **a)The research design outline**

A good research design should have these characteristics: eliminating deviation, avoiding confusion, controlling irrelevant variables, and testing the statistical accuracy of the hypothesis (Wellesma et al., 2010) . In addition, we must follow the basic theoretical knowledge of research and design. Therefore, the following is discussed in detail based on the research outline.

a) To establish a cause and effect relationship between the workshop and students ' written test performance.

The simplest experimental design

- i) Randomly select subjects from College students majoring in physical education.
- ii) Workshop group - receives treatment.
- iii) standard teaching - does not receive treatment.

b) When to use experimental procedures?

- i) Between the workshop and students have written test performance.
- ii) Control for all variables that might influence the outcome.
- c) Used when comparing workshop, and standard teaching group
  - i) Random assignment - assign individuals to random groups.
  - ii) Control over extraneous variables that might influence the relationship - influence in participant selection, procedures, statistics, or the design likely to affect the outcome.
  - iii) Manipulation of the treatment conditions - manipulate the workshop to determine the effect on the outcome.
  - iv) Outcome measures - assess whether the treatment conditions influence an outcome (Students' written test performance
  - vi) Group comparisons - compare students' written-test performance for different treatment.
- f) Guard against threats to validity - guard against false conclusions.

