Six weeks' content knowledge is the measurement content. In addition, the test content classification description is based on achievement tests. Achievement tests are divided into comprehensive achievement tests and single-subject achievement tests. Based on the 6-week content knowledge classification, the test belongs to the complete achievement test. Finally, the achievement test is compiled and analyzed. The establishment of achievement tests includes standard teachingized achievement tests and teacher's self-made achievement tests.

This research design is a standard teachingized test because this research achievement test was evaluated by six experts in the field of content knowledge. Six experts, including three American experts and three Chinese content knowledge experts, demonstrated. Three American experts are doctoral supervisors at Ohio State University, and they are essential researchers and discoverers of content knowledge.

ii) Choice is an true experiment.

The experimental control in actual experimental design strictly obeys the three basic principles of repetition, randomization, and local control. In addition, actual experiments comprise the most rigorous and robust experimental methods because of equating the groups through random assignment. In actual experiments, we randomly assign students to workshop groups and standard teaching groups. Individuals in the workshop group receive the experimental treatment, whereas those in the standard teaching group do not. After we administer the treatment, we compile average (or mean) scores on a posttest. One variation on this design is to

obtain pretest as well as posttest measures or observations. When we collect pretest scores, we will compare net scores (the differences between the pre-and post-test).

At the same time, in the design of the influence of 6 weeks' content knowledge on students' written test achievements, we must: a) Randomly select and allocate subjects. b) Accurately manipulate independent variables. c) Strictly control the effect of extra variables or evenly disperse interference variables.

Table 5. Two-way Breakdown of 6-weeks Content Knowledge Design

Content		CAQs	MAQs	T/F AQs	SAQs	EAQs	Knowledge	Understanding	Application	Analysis	Synthesis	Judgment	Score
Sports Training Design	Classify				√	√	-	-	5	5	5	-	15
	Application					√							
Basketball Class Hour Teaching Plan	Objectives				√	√	5	5	-	5	5	-	20
	Contents												
	Steps				√	√							

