### **13.Risk analysis of total failure in the data collection process.**

#### a) Validity and Reliability

Validity and reliability are two essential factors to consider when developing and testing any instrument (e.g., the effect of a 6-weeks content knowledge workshop on written test performance) for use in a study. Attention to these considerations helps ensure the quality of our measurement and the data collected for our research.

To start with, the reducing the risk of failure during data collection must analyze What is Reliability? The concept of reliability can be looked at from two sides:

i) Focus on the ability of an instrument to produce consistent measurements. The experiment mainly focuses on the written test, which must refer to the Education Examination Center and form a standard teachingized written test based on experts' evaluation in content knowledge.

ii) Focus on the degree of consistency in the measurements made by an instrument. Reliability only deals with the surface of the measure, regardless of precisely what it is measuring. Thus, a measure can be reliable without being valid.

iii) Concerns with consistency, replicability, dependability: Consistency – test the consistently yields the same score for an individual. Consistency mainly focuses on the surface of the workshop group and standard teaching group. Hence, consistency and reliability mainly deal with validity and reliability.

On the other hand, based on the 6-week content knowledge experiment, we must provide research to answer specific questions. We need to make a plan, outline it, or determine the strategy adopted to collect data. To achieve this goal, we must first clarify the independent variable workshop and the dependent variable students' written test achievements. Besides, other factors, such as validity, are necessary. Including internal validity, external validity, and construct validity. The specific analysis is as follows:

First, because it will confuse research results, it is not controlled and must be excluded. Especially extra variable, extra variable (confounding variables), embodied in students and teachers in the experiment. For example: when experimenting, the temperature of the weather, the mood of teachers and students, teachers month students' sleep and diet. We have no absolute control. But these impact factors happen so often that there is no need to control for them.

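### The aim is undivided written test achievement, but Table 12 lists six topic-level hypotheses, with no whole-test comparison between groups and none named primary

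*Protocol*

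**What the plan says.** **Aim.** The Executive Summary, repeated as section 14, wants to "find out which teaching method is more conducive to improving" students' written test achievement. It names no topic.

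**Dependent variable.** Section 13 a) says "we must first clarify the independent variable workshop and the dependent variable", which it then gives as students' written test achievements. Item iv) of the measures at the end of section 13 again seeks one inference, on the relation between the workshop and those achievements.

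**Group assignment.** Item i) of the same list ranks students by pretest score before assigning them to groups.

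**Comparison in the design text.** Section 2 a) plans to "compare students' written-test performance for different treatment". Section 2 b) says "After we administer the treatment, we compile average (or mean) scores on a posttest" and, where a pretest is taken, "we will compare net scores (the differences between the pre-and post-test". Neither place says whether the score is a total or a topic score.

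**Hypotheses.** Table 12 has three objectives (basic theoretical, health promotion and physical exercise knowledge) with two hypotheses each. All six concern a single topic. The last is "There is significant difference between the control group and the experimental group in the Referee rules written test performance among PE students in China".

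**Whole-test summaries.** Section 11.1 plans a mean and standard deviation for the theory test. Section 11.2 looks at the distribution of overall scores. Both are descriptive.

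**The concern.** The question asked and the hypotheses listed are at different levels. The question is which method gives better written test achievement. The hypotheses ask, six times, whether the groups differ on one topic. If the results are mixed, the protocol does not say which row or combination of rows answers the question, and the choice could be made after the results are known.

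Naming the primary hypothesis, and matching the hypotheses to the aim, belongs in a protocol. How topic results are adjusted or combined may properly sit in a statistical analysis plan, and its absence here is no part of this point.

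**Working it through.** **1. Text check.** The protocol has no figure to reproduce on this point. The rows of Table 12 are:

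| Hypothesis | Topic | Whole test? | Named primary? |
|---|---|---|---|
| 1.1 | Sports training design | No | No |
| 1.2 | Teaching design | No | No |
| 2.1 | Muscle function system | No | No |
| 2.2 | Exercise physiology system | No | No |
| 3.1 | Competition venue planning | No | No |
| 3.2 | Referee rules | No | No |

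That is six topic rows, no whole-test row and no primary. No other section names a primary outcome or hypothesis. This count carries the point; what follows only shows scale.

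**2. Assumptions for the illustration.**
- 52 students (section 10 a) iv), split 26/26. Section 13 assigns students equally to the groups.
- Two-sided 0.05 per test. The protocol states no alpha.
- Equal topic weights. The topic scores visible in Table 5 are 15, 20, 15 and 15, so this is only roughly true.
- A common inter-topic correlation r of 0.3, 0.5, 0.7 or 0.9.
- A two-group t-test with 50 degrees of freedom, standing in for the stated two-way ANOVA.

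**3. Same effect d in every topic.** The standardized effect on the total is d × √(6/(1+5r)). At d = 0.5 and r = 0.3 this is 0.5 × √(6/2.5) = 0.775. Noncentral t power:

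| d | One topic | Total, r = 0.3 | r = 0.5 | r = 0.7 | r = 0.9 |
|---|---|---|---|---|---|
| 0.5 SD | 42.4% | 78.2% | 63.9% | 53.3% | 45.5% |
| 0.8 SD | 80.7% | 99.2% | 95.9% | 90.4% | 84.0% |

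**4. Effect in one topic only.** The effect on the total is d/√(6+30r). At d = 0.8 it is 0.8/√15 = 0.207 for r = 0.3 and 0.8/√33 = 0.139 for r = 0.9. Power of the total-score test is then 11.3% down to 7.8%, against 80.7% for that topic's own test.

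**5. False positives, if one significant topic out of six were read as success.** The protocol sets no such rule. With independent topics the risk would be 1 − 0.95⁶ = 26.5%. At r = 0.3, 0.5, 0.7 and 0.9 it would be about 24%, 21%, 16% and 11%. One total-score test carries 5%.

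**The case against.** The strongest reply is that the six rows are the aim, broken down. Content knowledge is divided into six categories throughout, Table 5 scores by topic, and the objective column of Table 12 lists three knowledge areas that its hypotheses match. Each row compares the groups on part of written test performance. **This stands in part.** A reader might infer that the protocol leaves its own question untested by any hypothesis, and that goes too far. What remains is that no single hypothesis answers the undivided question and none is ranked first.

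A reader might also infer that the protocol commits itself to one overall test. Section 2 b) does say "the test belongs to the complete achievement test", and section 10 a) iii) says "the comprehensive tests of the six categories meet the comprehensive achievement test" standard. But section 10 a) iii) goes on to allow either a single test or a set of tests, and a set fits Table 12. Section 10 b) ii), on equality in the total average, is no support either: it sets equality of averages against mean difference and standard deviation, not a total score against topic scores. Likewise, the mean and net-score comparisons in section 2 could be made per topic, so they do not prove that an overall comparison was planned and then dropped.

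Finally, whether a total or a topic should lead is a design choice: steps 3 and 4 of the working favour opposite answers. **This stands too**, and it is a reason to state the choice in advance.

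**Conclusion.** The point holds in this limited form, and it should be fixed. The aim and dependent variable are undivided; Table 12 is split into six co-equal topic hypotheses, without a between-group comparison of the whole test or a named primary. An overall conclusion would have to be assembled from six results.

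This rests on the text alone. The figures depend on the listed assumptions. Under them, a total-score test has somewhat to much more power than any one topic test if the workshop helps all topics alike (45-78% against 42% at 0.5 SD), and far less if it helps one topic only (about 8-11% against 81% at 0.8 SD). The 11-26.5% false-positive range applies only under an any-topic success rule, which the protocol does not adopt.

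**What to change.** Add one hypothesis to Table 12: total written test score, workshop versus standard teaching, using the pretest total. A pretest-adjusted comparison such as ANCOVA would serve, or at least the net-score comparison described in section 2 b). Name it primary, rest the overall conclusion on it, and label the six topic hypotheses secondary. Any multiplicity adjustment can be stated there or in the statistical analysis plan. If the three objectives in Table 12 are the real targets, say so and reword the aim to match.

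The cost is wording plus one analysis of data already to be collected, with no extra students or tests. Single-topic results carry less weight and, if adjusted, face a stricter threshold: Holm's first step is 0.05/6 = 0.0083 at the assumed 0.05. Because the total would mostly miss a benefit confined to one topic, the six topic tests should stay in the plan.
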